8.6.2 Safety Analysis

Safety and tolerability will be assessed by clinical review of all relevant parameters including adverse events (AEs), laboratory tests, ECG, vital signs and body weight.

The ASaT population will be employed for safety analyses. Data after the initiation of rescue therapy will be excluded from the safety analyses for primary safety approach for double-blind period but those data will be included for the secondary safety approach for double-blind period. For long-term safety analyses, all data will be included in the analysis regardless of initiating the rescue therapy, since insulin dose during Phase B (open-label period) are allowed to down or up –titrate if clinically required .

Double-Blind Safety Assessment

The analysis of safety results in the double-blind period will follow a tiered approach ([Table 11](#)). The tiers differ with respect to the analyses that will be performed. Safety parameters or adverse events of special interest that are identified a priori constitute “Tier 1” safety endpoints that will be subject to inferential testing for statistical significance with p values and 95% CIs provided for between-group comparisons. Between-group comparisons will be made between active treatment groups versus placebo. Other safety parameters will be considered Tier 2 or Tier 3. Tier 2 parameters will be assessed via point estimates with 95% CIs provided for between-group comparisons; only point estimates by treatment group are provided for Tier 3 safety parameters.

Adverse events (overall summary, specific terms, system organ class terms, confirmed adjudicated pancreatitis) and predefined limits of change (PDLC) in laboratory parameters that are not pre-specified as endpoints of special interest will be classified as belonging to "Tier 2" or "Tier 3", based on the number of events observed. Membership in Tier 2 requires that at least 4 subjects in any treatment group exhibit the event or meet the PDLC criterion. All other adverse events and PDLCs will belong to Tier 3.

Because many 95% CIs may be provided without adjustment for multiplicity, the CIs should be regarded as a helpful descriptive measure to be used in review, and not as a formal method for assessing the statistical significance of the between-group differences in adverse events and PDLC.

Change from baseline in body weight at Week 16 will belong to Tier 2 and will be analyzed using a cLDA method described for HbA1c where imputation of missing data is model-based (i.e., accounting for missing data in an implicit fashion).

Continuous measures such as changes (or percent change) from baseline in laboratory, ECG, vital signs and body weight parameters that are not pre-specified as Tier-1 endpoints will be considered Tier 3 safety parameters. Summary statistics for baseline, on-treatment, and change (or percent change) from baseline values will be provided by treatment group in table format. Mean change (or Mean percent change) from baseline over time will be plotted. For safety endpoints except for body weight, all analyses will be based on the observed data (i.e., with no imputation of missing data).

[Table 11](#) summarizes the analysis strategy for safety endpoints. P-Values and 95% CIs for between-treatment differences (vs placebo) in the percentage of subjects with AEs of symptomatic hypoglycemia identified by the investigator (Tier 1), will be calculated using

M&N method [13]. For Tier 2 endpoints, 95% CIs for between-treatment differences will be provided using the M&N method.

Table 11 Analysis Strategy for Safety Parameters

Tier	Safety Endpoint	p-Value	95% CI for Treatment Comparison	Descriptive Statistics
Tier 1	Any AE of symptomatic hypoglycemia	X	X	X
Tier 2 ¹	AE overall summary		X	X
	Specific AEs ² , SOCs, confirmed pancreatitis and PDLCs		X	X
	Any AE of hypoglycemia		X	X
	Documented symptomatic		X	X
	Severe hypoglycemia		X	X
	Requiring medical assistance		X	X
	Not requiring medical assistance		X	X
Tier 3	Asymptomatic hypoglycemia		X	X
	Change from baseline in body weight at Week 16		X	X
Tier 3	All endpoints listed under Tier 2 (above) that have incidence <4 subjects in all treatment groups			X
	Additional hypoglycemia adverse event endpoints			X
	Change and percent change from baseline results (laboratory measurements, ECG and vital signs)			X

¹ Endpoints listed here will qualify for Tier 2 only if the incidence is ≥ 4 subjects in at least one of the treatment groups.
² Among those endpoints not prespecified as Tier 1 endpoints.
 SOC=System Organ Class; PDLC=Pre-Defined Limit of Change; X = results will be provided.

Hypoglycemia

The Tier 1 and Tier 2 hypoglycemia endpoints defined in Section 8.4.2 will be analyzed in the same ways described above. The Tier 3 summary of hypoglycemia will include the following, based on episodes classified by the investigator as adverse events:

- The numbers and percentages of subjects with each of the following, overall and by lowest reported glucose category (<50 mg/dL, ≤ 70 mg/dL, >70 mg/dL, or unknown). A subject's lowest glucose category will be classified as unknown only if no glucose measurements are available for that subject.
 1. any episodes (symptomatic or asymptomatic)
 2. symptomatic episodes
 3. asymptomatic episodes
- The numbers and percentages of subjects with episodes having precipitating factors, overall and separately by factor.
- The number of episodes per subject.

- The number of each of the following (summed across all subjects). The overall summary will include an indication of whether precipitating factors were present.
 1. all episodes (symptomatic or asymptomatic)
 2. symptomatic episodes
 3. asymptomatic episodes

A summary of subjects with episodes that were reported on the hypoglycemia assessment eCRF but were not classified by the investigator as adverse events, will also be provided. If a substantial number of subjects had episodes that were not classified as adverse events, then additional summaries may be provided for the Tier 3 analyses above, including all episodes reported on the hypoglycemia assessment eCRF (i.e., not restricted to adverse events). It is expected that all symptomatic hypoglycemia episodes will be classified by the investigator as adverse events and, thus, that any episodes that are not classified as adverse events will be asymptomatic episodes.

Long-Term Safety Assessment

For safety parameters at Week 52, the incidence rates of adverse or PDLC events and/or summary statistics on the continuous safety parameters will be calculated separately based on treatment received in the double-blind period. However, the safety results will only include the period that subjects are treated with omarigliptin. For subjects who were randomized to omarigliptin in the double-blind period, who continued to be administered omarigliptin in the open-label period (referred to as the omarigliptin/omarigliptin group), the results will be reported for whole duration of the study, Phase A and Phase B (i.e., 52-weeks). For subjects who were randomized to placebo in the double-blind period, who were switched to omarigliptin in the open-label period (referred to as the placebo/omarigliptin group), the results will be reported for the duration of omarigliptin administration in Phase B (i.e., 36-weeks). The between-groups comparisons and/or estimation of between-group difference will not be performed. Mean change from baseline in body weight up to Week 52 will be calculated by treatment group of double-blind period. The mean change will be computed relative to baseline (Visit 4/Day 1/Randomization).

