8.4.2 Safety Endpoints

The primary safety endpoint (i.e. Tier 1 safety endpoint) is the percentage of subjects experiencing one or more adverse events of symptomatic hypoglycemia, regardless of glucose value.

Other safety endpoints include adverse events, percentages of subjects meeting predefined limits of change in laboratory parameters (including blood chemistry and hematology), change (or percent change) from baseline at Week 16 and Week 52 in laboratory parameters, ECG, vital signs and body weight, and the numbers and percentages of subjects experiencing one or more of each the following:

- Adverse events of hypoglycemia (symptomatic or asymptomatic)
- Documented symptomatic hypoglycemia: An episode with clinical symptoms attributed to hypoglycemia with a documented glucose level of ≤ 70 mg/dL.
- Severe hypoglycemia, defined as adverse events of symptomatic hypoglycemia that required assistance, either medical or non-medical, regardless of whether such assistance was obtained. These events will be further sub-classified as:
 - Those that required medical assistance. Adverse events of symptomatic hypoglycemia that included a markedly depressed level of consciousness, loss of consciousness, or seizure will be classified as having required medical assistance, whether or not medical assistance was obtained.
 - Those that did not require medical assistance. (i.e., those episodes that required non-medical assistance to treat).
- Asymptomatic hypoglycemia: An episode with a documented glucose level of ≤ 70 mg/dL but without clinical symptoms attributed to hypoglycemia.

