The probability of observing at least one specific adverse event in this study depends on the number of subjects and the underlying percentage of subjects with a specific adverse event in the study population. If the underlying incidence of a specific adverse event is 1%, there is a 70% and 45% chance of observing at least one specific adverse event among 120 and 60 subjects, respectively. If no adverse events are observed among the 120 and 60 subjects, this study will provide 95% confidence that the underlying percentage of subjects with an adverse event is <2.5% and <4.9%, respectively.

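### The four-subject rule for Tier 2 also governs harms named in advance, so severe hypoglycemia and confirmed pancreatitis can be reported without a between-group confidence interval

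*Combined protocol and SAP*

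**What the plan says.** Section 8.6.2 sorts the double-blind safety endpoints into three tiers. Tier 1 holds only adverse events of symptomatic hypoglycemia and always gets a p-value and a 95% CI. Tier 2 gets a between-group 95% CI by the Miettinen-Nurminen (M&N) method. For the rest, "only point estimates by treatment group are provided for Tier 3 safety parameters".

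The boundary between Tier 2 and Tier 3 is a count of subjects: "Membership in Tier 2 requires that at least 4 subjects in any treatment group exhibit the event or meet the PDLC criterion". The list of events sorted in this way reads "Adverse events (overall summary, specific terms, system organ class terms, confirmed adjudicated pancreatitis", so pancreatitis is expressly included.

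Table 11 lists under Tier 2 several endpoints that section 8.4.2 defines in advance, such as "Severe hypoglycemia, defined as adverse events of symptomatic hypoglycemia that required assistance", together with its two subtypes and documented symptomatic hypoglycemia. Footnote 1 makes them all conditional on the same count: "Endpoints listed here will qualify for Tier 2 only if the incidence is ≥ 4 subjects in at least one of the treatment groups". The Tier 3 row of the table takes the remainder: "All endpoints listed under Tier 2 (above) that have incidence <4 subjects in all treatment groups".

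Sections 8.1 and 8.9 give 120 subjects on omarigliptin and 60 on placebo. Section 8.6.2 describes the safety CIs as a descriptive aid to review, without multiplicity adjustment.

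**The concern.** A count threshold is a reasonable way to keep a long adverse event table readable. It suits harms named in advance less well. Those endpoints were chosen for their clinical importance, and they may well be rare. For a rare harm the useful statement is how large an excess the data can exclude, and that is the statement the rule withholds when counts are low. Safety and tolerability are primary objectives (section 3.1), section 4.2.1 describes the trial as a pharmacovigilance activity, and pancreatitis is the one event sent to the adjudication committee (section 7.3.1).

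There is a secondary matter. The threshold is the same number of subjects in each arm, but one arm is twice the size of the other. Four subjects are 4/120 = 3.3% on omarigliptin and 4/60 = 6.7% on placebo. Among uncommon events, the larger arm will therefore usually be the one that carries an event into Tier 2.

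**Working it through.** **Inputs.** Arm sizes are 120 and 60 (section 8.9). The threshold is 4 subjects in either arm (section 8.6.2 and Table 11, footnote 1). The interval is M&N, 95% (section 8.6.2). The documents give no incidence for severe hypoglycemia or pancreatitis, so rates are assumed and a range is shown. The plan's own illustrative incidence for an adverse event is 1% (section 8.9).

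**The plan's figures.** Section 8.9 states a 70% and 45% chance of at least one event at 1% incidence. The formula 1 - 0.99^n gives 0.701 for n = 120 and 0.453 for n = 60. It also states zero-event bounds of 2.5% and 4.9%. The formula 1 - 0.05^(1/n) gives 2.47% and 4.87%. Both pairs reproduce.

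**Chance that a named harm gets no CI.** With X ~ Bin(120, p) on omarigliptin and Y ~ Bin(60, p) on placebo, this is P(X ≤ 3) × P(Y ≤ 3).

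| True rate, both arms | P(X ≤ 3) | P(Y ≤ 3) | P(no CI) |
|---|---|---|---|
| 1% | 0.967 | 0.997 | 96% |
| 2% | 0.780 | 0.968 | 75% |
| 3% | 0.513 | 0.894 | 46% |
| 5% | 0.144 | 0.647 | 9% |

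The chance is 50% at a rate of about 2.9%. With unequal rates it is 78% for 2% on omarigliptin against 1% on placebo, and 51% for 3% against 1%.

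**What the missing intervals would show.** These are M&N 95% limits for omarigliptin minus placebo, in percentage points.

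- 3/120 against 0/60: difference 2.5, CI -3.6 to +7.1.
- 1/120 against 0/60: difference 0.8, CI -5.2 to +4.6.
- 0/120 against 0/60: difference 0, CI -6.0 to +3.1. Here the limits have a closed form. With c = 1.96² × (180/179)/n, each limit is c/(1 + c) in size. For n = 60, c = 0.0644 and the lower limit is -6.05. For n = 120, c = 0.0322 and the upper limit is +3.12.

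The method gives an interval at any count, including none.

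**Secondary point: selection under 2:1 allocation.** With the same true rate in both arms, enumerate all (X, Y), keep those with X ≥ 4 or Y ≥ 4, and take the mean of X/120 - Y/60 among them.

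| True rate | Reaches Tier 2 | Mean difference given Tier 2 | Omarigliptin higher / placebo higher | Share with a CI if count is over both arms |
|---|---|---|---|---|
| 1% | 3.6% | +1.85 points | 83% / 10% | 10.8% |
| 2% | 24.5% | +1.10 points | 68% / 20% | 48.6% |
| 3% | 54% | +0.60 points | 58% / 29% | 79% |
| 5% | 91% | +0.13 points | 49% / 41% | 98% |

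With the rule X + Y ≥ 4 the mean difference among selected events is 0. Given the total T and equal rates, the expected value of X/120 and of Y/60 is T/180 in each case.

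The display is also uneven. A result of 4/120 against 0/60 gets a CI, which includes zero (-2.8 to +8.3). A result of 0/120 against 3/60 gets none, although its CI excludes zero (-13.7 to -1.7).

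**The case against.** The strongest reply is that little is lost. Tier 3 still reports these endpoints by arm, and section 8.4.2 promises numbers and percentages. A reader might infer that a result such as 3 against 0 could not be stated with its uncertainty. The documents do not support that, because anyone holding the counts can compute the interval. What is missing is a planned, reported CI. This stands as a limit on the size of the point. It does not explain why a harm defined in advance should lose its interval because it turned out rare.

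A reader might also see a contradiction with section 8.9, which says: "If no adverse events are observed among the 120 and 60 subjects, this study will provide 95% confidence that the underlying percentage" lies below a stated bound. There is none. Those bounds are for one arm with zero events, they need only the count, and section 8.9 promises no between-group interval.

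Nor does the plan hide a clear harm signal where placebo has no cases. The largest undisplayed excess of that kind is 3 against 0, and its CI includes zero. Severe hypoglycemia is also a subset of the Tier 1 endpoint, which is always tested. Both statements are right, but a CI for all symptomatic events does not bound the severe ones.

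On the secondary point, a reader might conclude that the safety analysis is biased against omarigliptin. That goes too far. Every event is tabulated by arm and no event's estimate changes. The shift is an average over only those events that cross the threshold, and it almost vanishes at 5%. A combined count also has a price: it triples the share of events with a CI at 1% and doubles it at 2%. Reasonable statisticians could differ on that threshold.

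**Conclusion.** The main point holds as a reporting gap. As written, severe hypoglycemia, its subtypes, the other hypoglycemia endpoints of section 8.4.2 placed under the count, and confirmed pancreatitis lose their planned between-group CI whenever each arm has fewer than four cases. How often this happens depends on rates that the documents do not give. It is the likelier outcome below about 2.9% with equal rates, and uncommon at 5%, so an unqualified claim that the CI is usually lost would be unsupported. The calculation assumes arms of exactly 120 and 60 and independent subjects.

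The secondary point holds as a display effect: at low incidence and equal true rates, the events shown with CIs lean towards an omarigliptin excess, by +1.85 points on average at 1% and +0.13 at 5%.

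Neither point touches the primary efficacy result, the Tier 1 endpoint or the data collected.

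**What to change.** In section 8.6.2 and Table 11, exempt the hypoglycemia endpoints of section 8.4.2 and confirmed adjudicated pancreatitis from footnote 1, so that their M&N difference and 95% CI are always reported. The cost is a sentence in the text, an edit to the footnote, and a few wide intervals that the plan already labels as descriptive. No new data are needed.

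For the remaining adverse events and laboratory limits, the sponsor may consider a threshold of four subjects over the two arms together. Everything now in Tier 2 would stay there and the mean shift would go. The share of events given a CI would rise from 3.6% to 10.8% at 1%, from 24.5% to 48.6% at 2%, and from 54% to 79% at 3%. If the present threshold is kept, a note beside the Tier 2 table should say that, under 2:1 allocation, rare events selected by this count tend by chance to show an excess on omarigliptin.

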8.4 Analysis Endpoints

Efficacy and safety endpoints that will be evaluated for within- and/or between-treatment differences are listed below.

The baseline value will be defined as the Visit 4/Day 1/Randomization measurement. If this measurement is not available, the Visit 3/Week -2 measurement will be used as the baseline value. If neither measurement is available, the baseline value will be treated as missing. The primary time point is Week 16.

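### For the placebo/omarigliptin group, long-term body-weight change is measured from Visit 4 and so includes 16 placebo weeks, although 8.6.2 limits long-term safety results to time on omarigliptin

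*Combined protocol and SAP*

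**What the plan says.** The long-term part of 8.6.2 opens with a scope that goes beyond event counts: "summary statistics on the continuous safety parameters will be calculated separately based on treatment received in the double-blind period". It then sets the limit: "the safety results will only include the period that subjects are treated with omarigliptin". For subjects who switch from placebo, "the results will be reported for the duration of omarigliptin administration in Phase B (i.e., 36-weeks").

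The paragraph closes with a rule for one parameter: "Mean change from baseline in body weight up to Week 52 will be calculated by treatment group of double-blind period". Its reference point is explicit: "The mean change will be computed relative to baseline (Visit 4/Day 1/Randomization"). No separate reference is given for the switched group, and body weight is not called an exception.

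Two other places bear on this. Section 8.4 covers both kinds of endpoint ("Efficacy and safety endpoints that will be evaluated for within- and/or between-treatment differences are listed below") and supplies one baseline: "The baseline value will be defined as the Visit 4/Day 1/Randomization measurement", with Visit 3/Week -2 as fallback. Section 8.4.2 makes safety endpoints of "change (or percent change) from baseline at Week 16 and Week 52 in laboratory parameters, ECG, vital signs and body weight".

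**The concern.** For the omarigliptin/omarigliptin group, Visit 4 is the start of omarigliptin, so the two instructions agree. For the placebo/omarigliptin group, Visit 4 is the start of placebo. A change from Visit 4 to any Phase B visit therefore contains whatever happened to weight during Phase A on placebo.

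Safety and tolerability for up to 52 weeks is a primary objective (3.1, objective 3). A reader told that this group's long-term safety results cover 36 weeks on omarigliptin could take the weight change as a change on omarigliptin. Section 8.11 shows that the restriction was meant to carry through: it declines to summarize whole-study compliance for the placebo group so as to match the safety assessments.

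**Working it through.** **Inputs.** Phase A is 16 weeks and Phase B 36 weeks (2.1). About 60 subjects are randomized to placebo out of 180 (8.9). The 15% discontinuation rate over 52 weeks is stated for the omarigliptin group (8.9); applying it to placebo is an assumption. The Visit 8 window is -6 days (6.0). Visit procedures come before the first open-label dose (5.2.2.2). A missed dose may be taken up to the day before the next scheduled one (5.2.2.3).

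**The plan's own figure.** 52 - 16 = 36 weeks on omarigliptin for the switched group. This reproduces.

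**What the Visit 4-based change contains.** For each subject with all three values:

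(Week 52 - Visit 4) = (Week 16 - Visit 4) + (Week 52 - Week 16)

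The first term on the right is the placebo-phase change and enters one for one. The placebo share of the window is 16/52 = 112/364 days = 30.8%. This is a share of time, not a measure of bias.

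**Size in kilograms.** The discrepancy equals the mean placebo-phase change in the same subjects, which the documents do not give. As an illustration with assumed values, take a Phase B change of +0.5 kg:

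| Placebo-phase change (assumed) | Change from Visit 4 | Change from Week 16 |
|---|---|---|
| -1.0 kg | -0.5 kg | +0.5 kg |
| -0.5 kg | 0.0 kg | +0.5 kg |
| 0 kg | +0.5 kg | +0.5 kg |
| +0.5 kg | +1.0 kg | +0.5 kg |
| +1.0 kg | +1.5 kg | +0.5 kg |

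**Placebo time left with a Week 16 reference.** Visit 8 can fall up to 6 days before the scheduled first open-label dose, and that dose can be up to 6 days late, so up to 12 days may precede omarigliptin. With Week 52 at its nominal day, the longest window is 252 + 6 = 258 days, so the share is 0 to 12/258 = 4.7%.

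**Can the Phase B change be recovered by subtraction?** Approximately. About 60 x (1 - 0.15) = 51 switched subjects would have Week 52 data, under the assumption above. If the model-based Week 16 estimate stands for all 60, it differs from the mean of the 51 by (9/60) x d = 0.15d, where d is the difference in placebo-phase change between the 9 who leave and the 51 who stay. For an assumed d of 1 kg, the error is 0.15 kg.

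**Other continuous parameters.** Section 8.4.2 makes Week 52 change an endpoint for laboratory tests, ECG and vital signs. The long-term text in 8.6.2 gives them no baseline. Section 8.4 offers only Visit 4 or its fallback, so the same mismatch follows by default.

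**The case against.** The best defence is that the two statements govern different things: the restriction fixes which period is reported, and the closing sentences fix the reference value for one parameter. A specific rule following a general one may be deliberate. The Visit 4 sentence also appears in the long-term efficacy text of 8.6.1, so the sponsor may have wanted Week 52 weight on the same footing as Week 52 HbA1c and FPG. A programmer would know what to compute. This stands as a possible intention, but the text does not state it. It also leaves the arithmetic alone: even if only Phase B visits are displayed, a change from Visit 4 still includes the placebo weeks.

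Three stronger readings are tempting and are not supported.

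- A reader might infer that the Phase B change cannot be recovered because the double-blind analysis drops post-rescue data while the long-term summary keeps it. Section 8.6.2 also plans a secondary double-blind approach that keeps those data, which largely removes that obstacle. Dropout between Week 16 and Week 52 is the main one left.
- A reader might infer an explicit contradiction for every continuous safety parameter. It is explicit only for body weight. For laboratory tests, ECG and vital signs it rests on the 8.4 default. Predefined limits of change are affected only if some are defined relative to baseline, which the documents do not say.
- A reader might infer that the long-term safety results as a whole are contaminated. Adverse event incidence for the switched group is counted over Phase B and needs no baseline value.

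A Week 16 reference also has drawbacks. It follows any Phase A insulin change, and it puts two reference points in one display. That argues for showing both figures, not for replacing the Visit 4 one.

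**Conclusion.** The inconsistency is real and explicit for body weight in the placebo/omarigliptin group, about 60 of 180 randomized subjects. For the other continuous safety parameters it is an inference from the general baseline definition. The discrepancy equals the mean placebo-phase change in the subjects summarized; its size and sign are unknown, and the kilogram values used here are assumptions. The 51 subjects at Week 52 assume that the stated discontinuation rate also holds for placebo.

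The consequence is limited. The summaries are descriptive and no between-group comparison is planned at Week 52. No hypothesis, test, power or sample size changes. The omarigliptin/omarigliptin group and Week 52 HbA1c and FPG are unaffected. The correction is still worth making, because as written the figure does not match the period the plan says it reports.

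**What to change.** Add to the long-term part of 8.6.2, with a cross-reference in 8.4:

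*For the placebo/omarigliptin group, long-term change and percent change in body weight, laboratory tests, ECG and vital signs, and any predefined limit of change that is relative to baseline, are reported relative to the last value before the first open-label omarigliptin dose (normally Visit 8/Week 16). The change from Visit 4 is shown alongside and labelled as an exception that includes 16 weeks on placebo.*

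A footnote should say that the Week 16-based change is uncontrolled, starts after any Phase A insulin change and includes Phase B insulin adjustments.

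These are non-confirmatory summaries, so the supplemental SAP described in 8.0 would also serve. Either way, the rule should be fixed before the Week 16 unblinding in 8.2. After that the placebo-phase change is known and the choice of reference could look data-driven.

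The cost is one derived baseline variable, a few lines of text, a few extra descriptive tables and the presence of two reference points in the display. No new visits or measurements are needed, because Week 16 change is already an endpoint for these parameters (8.4.2). Week 52 HbA1c and FPG need no change.
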